4.5.2 Main analytical approach

Exploratory efficacy endpoints will be analyzed using the same methodology as above for similar data (continuous, proportion, or time to event).

Time to first UAS7 change from baseline of ≥ 9.5 and ≥ 10.5 will be analyzed similar to time to ISS7 MID (ISS7 ≥ 5) response. For participants not receiving selected prohibited medications and/or rescue medications, all available data up to Week 24 (ie, Day 169) including those collected during the off-treatment period will be used. Participants without events will be censored at Day 169 or their last UAS7 assessment date on or before Day 169 if discontinued from the study, whichever is earlier.

4.6 MULTIPLICITY ISSUES

A multiplicity procedure is proposed to control the overall type-I error rate for testing the primary and selected secondary endpoints. The overall type-I error is controlled at 0.05. The comparisons with placebo will be tested based on the hierarchical order below at 2-sided $\alpha = 0.05$.

1. Change from baseline in ISS7 at Week 24
2. Change from baseline in UAS7 at Week 24
3. Change from baseline in HSS7 at Week 24
4. Proportion of patients with MID (ISS7 ≥ 5) response at Week 24
5. Proportion of patients with UAS7 ≤ 6 at Week 24
6. Proportion of patients with UAS7 = 0 at Week 24
7. Change from baseline in UCT at Week 24

In EU and EU reference countries:

1. Change from baseline in UAS7 at Week 24
2. Change from baseline in ISS7 at Week 24
3. Change from baseline in HSS7 at Week 24
4. Proportion of patients with MID (ISS7 ≥ 5) response at Week 24
5. Proportion of patients with UAS7 ≤ 6 at Week 24
6. Proportion of patients with UAS7 = 0 at Week 24
7. Change from baseline in UCT at Week 24

Study C is considered positive when the primary endpoint (change from baseline in ISS7 at Week 24 in non-EU countries or change from baseline in UAS7 at Week 24 in EU and EU reference countries) achieves statistical significance.

4.7 SAFETY ANALYSES

All safety analyses will be performed on the safety population as defined in [Section 3](#), unless otherwise specified, using the following common rules:

- The analysis of the safety variables will be essentially descriptive, and no testing is planned.
- Safety data in participants who do not belong to the safety population (eg, exposed but not randomized) will be provided separately.

4.7.1 Extent of exposure

The extent of IMP exposure will be assessed by the duration of IMP exposure and compliance and summarized within the safety population.

Duration of IMP exposure

Duration of IMP exposure is defined as last dose date – first dose date + 15 days (or +29 days for children < 30 kg), regardless of unplanned intermittent discontinuations. If the date of the last dose of IMP is missing, the duration of IMP will be left as missing.

Duration of IMP exposure will be summarized descriptively as a quantitative variable (number, mean, SD, median, minimum, and maximum). In addition, duration of IMP exposure will also be summarized categorically by numbers and percentages for each of the following categories and cumulatively according to these categories:

- >0 and \leq 2 weeks
- >2 and \leq 4 weeks
- >4 and \leq 8 weeks
- >8 and \leq 12 weeks
- >12 and \leq 16 weeks
- >16 and \leq 20 weeks
- >20 and \leq 24 weeks
- >24 weeks and \leq 24 weeks + 3 days
- >24 weeks + 3 days

Additionally, the cumulative duration of IMP exposure will be provided, defined as the sum of the duration of treatment exposure for all participants, and will be expressed in participant years.

Treatment compliance

A given administration will be considered noncompliant if the participant did not take the planned dose as required by the protocol. No imputation will be made for participants with missing or incomplete data.

Percentage of treatment compliance for a participant will be defined as the number of administrations that the participant was compliant divided by the total number of administrations that the participant was planned to take from the first administration of IMP up to the actual last administration of IMP.

Treatment compliance will be summarized quantitatively and categorically: <80%, \geq 80%.

Cases of overdose (defined as at least twice the intended dose during an interval of less than 11 days (or less than 25 days for children < 30 kg) will be summarized.

4.7.2 Adverse events

General common rules for adverse events

All adverse events (AEs) will be coded to a lower-level term (LLT), preferred term (PT), high-level term (HLT), high-level group term (HLGT), and associated primary system organ class

(SOC) using the Medical Dictionary for Regulatory Activities (MedDRA) version currently in effect at Sanofi at the time of database lock.

The AEs will be analyzed in the following 3 categories:

- Pre-treatment AEs: AEs that developed, worsened or became serious during the pre-treatment period.
- Treatment-emergent adverse events (TEAE)s: AEs that developed, worsened or became serious during the treatment-emergent period.
- Post-treatment AEs: AEs that developed, worsened or became serious during the post-treatment period.

Similarly, deaths will be analyzed in the pre-treatment, treatment-emergent and post-treatment periods.

The primary focus of AE reporting will be on TEAEs. Pre-treatment and post-treatment AEs will be described separately.

An AE with incomplete or missing date/time of onset (occurrence, worsening, or becoming serious) will be classified as a TEAE unless there is definitive information to determine it is a pre-treatment or a post-treatment AE. If the day is missing, it will be imputed using 01 (except if the same month and year of 1st IMP, then the day of first IMP will be used). If month is missing, the AE start date will remain missing.

If the assessment of the relationship to IMP is missing for an AE, this AE will be assumed as related to IMP. If the severity is missing for 1 of the treatment-emergent occurrences of an AE, the severity will be imputed with the maximal severity of the other occurrences. If the severity is missing for all the occurrences, the severity will be left as missing.

Multiple occurrences of the same event in the same participant will be counted only once in the tables within a treatment phase.

The AE tables will be sorted as indicated in [Table 5](#).

Table 5 - Sorting of AE tables

| AE presentation | Sorting rules |
|------------------------|---|
| SOC, HLT and PT | By the internationally agreed SOC order and by alphabetic order of HLTs, HLTs and PTs. |
| SOC, HLT and PT | By the internationally agreed SOC order and by alphabetic order of HLTs and PTs. |
| SOC and PT | By the internationally agreed SOC order and decreasing frequency of PTs ^{a, b} |
| SMQ/CMQ and PT | By decreasing frequency of SMQs/CMQs and PTs ^a |
| PT | By decreasing frequency of PTs ^a |

^a Sorting will be based on the SAR231893 dupilumab group

^b The table of all TEAEs presented by SOC and PT will define the presentation order for all other tables (eg, treatment-emergent SAE) presented by SOC and PT, unless otherwise specified.

Analysis of all adverse events

The overview of TEAE with the details below will be generated:

- Any TEAE
- Any severe TEAE
- Any treatment emergent SAE
- TEAE leading to death
- Any TEAE leading to permanent intervention discontinuation
- Any treatment emergent AESI
- Any treatment emergent other AE grouping
- Any TEAE related to IMP

The AE summaries of [Table 6](#) will be generated with number (%) of participants experiencing at least one event.

Table 6 - Analyses of adverse events

| Type of AE | MedDRA levels |
|--|---|
| All TEAE | Primary SOC, HLGT, HLT and PT |
| | Primary SOC and PT |
| | PT |
| | Primary and secondary SOC, HLGT, HLT and PT |
| Common TEAE ($\geq 2\%$ and $\geq 5\%$ in any group) | Primary SOC and PT |
| TEAE related to IMP as per Investigator's judgment | Primary SOC, HLGT, HLT and PT |
| | Primary SOC and PT |
| TEAE by maximal intensity | Primary SOC and PT |
| Treatment emergent SAE | Primary SOC, HLGT, HLT and PT |
| | Primary SOC and PT |
| Treatment emergent SAE related to IMP as per Investigator's judgment | Primary SOC, HLGT, HLT and PT |
| TEAE leading to permanent intervention discontinuation | Primary SOC, HLGT, HLT and PT |
| | Primary SOC and PT |
| TEAE leading to death (death as an outcome of the AE as reported by the Investigator in the AE page) | Primary SOC, HLGT, HLT and PT |
| Pretreatment AE | Overview ^a |
| | Primary SOC and PT |

^a Will include the following AE categories: any AEs, any serious AEs, any AEs leading to death, any AEs leading to permanent intervention discontinuation

In addition, the exposure adjusted incidence rate of TEAEs by primary SOC and PT will be generated, showing the number of participants with at least one TEAE per 100 patient-years. For participants with an event, patient-years will be calculated up to the first event, and for participants without an event, patient-years will correspond to the length of the TE period.

Risk differences (constructed using the Miettinen and Nurminen method) and hazard ratios (Cox proportional hazards model) for dupilumab versus placebo with corresponding 95% CIs will be provided for the overview table, and common TEAEs (PT $\geq 2\%$ in any intervention group).

Participants without an event will be censored at the end of the treatment-emergent period in the Cox model. Forest plots will also be presented.

Analysis of deaths

In addition to the analyses of deaths included in [Table 5](#) the number (%) of participants in the following categories will be provided:

- Deaths during the treatment-emergent and post-treatment periods
- Deaths in non-randomized or randomized but not treated participants

Analysis of adverse events of special interest (AESIs) and other AEs of interest

Adverse events of special interest (AESIs) and other AEs of interest will be selected for analyses as indicated in [Table 7](#). Number (%) of participants experiencing at least one event will be provided for each event of interest. Tables will be sorted as indicated in [Table 5](#).

Table 7 - Selections for AESIs and other AEs of interest

| AE Grouping | Criteria |
|---|--|
| AESI | |
| Anaphylactic reaction | Anaphylactic reaction algorithmic approach (Introductory Guide for Standardised MedDRA Queries (SMQs) Version 18.1): includes anaphylactic reaction narrow SMQ (20000021) terms and programmatic identification of cases based on occurrence of at least two preferred terms meeting the algorithm criteria occurring within 24 hours of each other. The latter cases identified using the algorithm will undergo blinded medical review taking into account the timing of events relative to each other and to IMP administration for final determination of an anaphylactic reaction or not. |
| Systemic hypersensitivity reactions | SMQ [20000214] hypersensitivity narrow search and [AE corrective treatment/therapy = 'Y' or Action taken with IMP = 'Drug withdrawn' or Action taken with IMP = 'Drug interrupted'] followed by blinded medical review (documented process) for selection of relevant systemic hypersensitivity events. |
| Helminthic infections | CMQ10544 based on HLT as "Helminthic disorder". |
| Any severe type of conjunctivitis | CMQ10498 based on PTs (See Section 5.6 ^a) and "Severe" ticked in Adverse Events eCRF page. |
| Any severe type of blepharitis | CMQ10497 based on HLT as "Lid, lash and lacrimal infections, irritations and inflammations" and "Severe" ticked in Adverse Events eCRF page. |
| Keratitis | CMQ10642 based on the following PTs [keratitis, allergic keratitis, ulcerative keratitis, atopic keratoconjunctivitis, herpes ophthalmic, ophthalmic herpes simplex, corneal infection] ^a . |
| Clinically symptomatic eosinophilia (or eosinophilia associated with clinical symptoms) ^b | CMQ10641 (based on HLT = Eosinophilic disorders or PT = Eosinophil count increased) and AESI is "Yes". |
| Pregnancy of a female patients entered in a study as well as pregnancy occurring in a female partner of a male patient entered in a study with IMP/NIMP | "Pregnancy" or "Partner Pregnancy" checked on the Pregnancy eCRF page as reported by the investigator. |

| AE Grouping | Criteria |
|--|---|
| Significant ALT elevation | ALT >5 × ULN in participants with baseline ALT ≤2 × ULN; OR ALT >8 × ULN if baseline ALT >2 × ULN. |
| Symptomatic overdose with IMP | Symptomatic Overdose is answered Yes, with Overdose of IMP answered Yes on AE eCRF.. |
| Symptomatic overdose with NIMP | Symptomatic Overdose is answered Yes, with Overdose of NIMP answered Yes on AE eCRF.. |
| Other selected AE Grouping | |
| Serious injection site reactions or severe injection site reactions that last longer than 24 hours | HLT = 'Injection site reactions' and either with serious status, or with severe status and (AE end date/time - AE start date/time) ≥24 hours or ongoing. |
| Severe or serious infection | Primary SOC = 'Infections and infestations' and with severe or serious status. |
| Drug-related hepatic disorder | SMQ [20000006] Drug-related hepatic disorders- narrow. |
| Injection site reaction | HLT = 'Injection site reactions'. |
| Malignancy | SMQ [20000091]- Malignant or unspecified tumors narrow. |
| Conjunctivitis (narrow) | CMQ10644 based on the following PTs [Conjunctivitis, Conjunctivitis allergic, Conjunctivitis bacterial, Conjunctivitis viral, Atopic keratoconjunctivitis] ^a . |
| Conjunctivitis (broad) | CMQ10645 based on the following PTs [Conjunctivitis, Conjunctivitis allergic, Conjunctivitis bacterial, Conjunctivitis viral, Atopic keratoconjunctivitis, Blepharitis, Dry eye, Eye irritation, Eye pruritus, Lacrimation increased, Eye discharge, Foreign body sensation in eyes, Photophobia, Xerophthalmia, Ocular hyperaemia, Conjunctival hyperaemia] ^a . |
| Conjunctivitis (FDA) | CMQ10643 based on the following PTs [Conjunctivitis, Conjunctivitis allergic, Conjunctivitis bacterial, Conjunctivitis viral, Eye irritation, Eye inflammation, Giant papillary conjunctivitis] ^a . |
| Keratitis (FDA) | CMQ30102 based on the following PTs [keratitis, allergic keratitis, ulcerative keratitis, atopic keratoconjunctivitis, ophthalmic herpes simplex] ^a . |

a The list of terms may be adjusted according to MedDRA version changes

b All cases of Eosinophilia will be included in the analysis, where cases associated with clinical symptoms will be further described in the CSR

The following summaries will be provided:

- All TEAEs, by selected standardized MedDRA query (SMQ)/Customized MedDRA query (CMQ) and PT or by laboratory values (as in alanine aminotransferase (ALT) elevation), showing the number (%) of participants with at least 1 PT,
- The exposure adjusted incidence rate by selected SMQ/CMQ and PT showing the number of participants with at least one TEAE per 100 patient-years,
- All TEAEs, by selected SMQ/CMQ including risk differences and hazard ratios with corresponding 95% CIs for each AESI and other selected AE groupings:
 - Number (%) of participants with any specific TEAE,
 - Number (%) of participants with any specific serious AE (regardless of treatment emergent status),
 - Number (%) of participants with any specific treatment emergent serious AE,
 - Number (%) of participants with any specific AE leading to death,

- Number (%) of participants with any specific TEAE leading to permanent study drug discontinuation,
- Number (%) of participants with any specific TEAE related to IMP reported by investigator,
- Number (%) of participants with any specific TEAE by maximum intensity, corrective treatment, and final outcome,
- Number (%) of participants with any specific TEAE adjusted by the exposure duration,
- Time to onset of first TEAE and cumulative incidence at specified time points (K-M estimates at Week 12 and 24 and K-M plot may be provided to depict the course of onset over time if the number of events is large enough),
- Number (%) of participants with injection site reactions to the related injection,
- Number (%) of participants with different number of injection site reactions.
- In addition, AESIs reported by the investigator in eCRF will be summarized separately.

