4 STATISTICAL ANALYSES

4.1 GENERAL CONSIDERATIONS

This SAP provides a comprehensive and detailed description of strategy and statistical techniques for the summary and analysis of EFC16461 Study C (omalizumab naïve) only. Study A (omalizumab naïve) and Study B (omalizumab intolerant or incomplete responders) were summarized separately in different SAPs.

In general, continuous data will be summarized using the number of observations available, mean, standard deviation (SD), median, minimum, and maximum. Categorical and ordinal data will be summarized using the count and percentage of participants.

The baseline value of efficacy parameters is defined as the last available value up to randomization date and prior to the first dose of study medication unless otherwise specified. The baseline value of the other parameters is defined as the last available value prior to the first dose of investigational medicinal product (IMP) if the participant is treated, or the last available value up to randomization date if the participant is not exposed to IMP.

Observation period

The observation period will be divided into 4 segments:

- The **pre-treatment period** is defined as the period up to first IMP administration.
- The **treatment-emergent (TE) period** is defined as the period from the first IMP administration to the last IMP administration + 98 days. The treatment-emergent period includes the following 2 periods:
 - The **on-treatment period** is defined as the period from the first IMP administration to the last administration of the IMP + 14 days (+28 days for children <30 kg)
 - The **residual treatment period** is defined as the period from the end of the on-treatment period to the end of the treatment-emergent period.
- The **post-treatment period** is defined as the period from the end of the treatment-emergent period.

The on-study observation period is defined as the time from start of intervention until the end of the study defined as the status date collected on e-CRF page “Completion of End of Study”.

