For time to participants receiving first OCS for CSU during the planned treatment period, participants who receive selected prohibited medications and/or rescue medications other than OCS for CSU, data prior to start of the medication will be used, but after medication start, the participant will be censored at time of start of medication. Participants who don't receive OCS during the treatment period will be censored at Day 169 or their status date collected on the completion of study/follow-up eCRF form, whichever is earlier. This endpoint will be analyzed using a Cox proportional hazards model, including intervention, presence of angioedema at baseline, and region as covariates.

Categorical summaries by visit will be provided for PGIC and PGIS.

In addition, secondary endpoints included in the multiplicity procedure ([Section 4.6](#)) will be analyzed in the subgroup of adults and adolescent participants.

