4.9 INTERIM ANALYSES

No interim analysis is planned.

For Study C, a primary database lock will be performed when all randomized participants in this study have completed their 24-week treatment phase. Analysis will be based on all data collected up to this database lock and will be considered as the final analyses in the Study C CSR.

The database will be updated at the end of the study for all participants to include the post-treatment follow-up information and updates for the events previously ongoing at the time of the primary lock. Additional data between this database lock and last participant completing last visit will be summarized in a CSR addendum.

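### Study C SAP 4.7.2 credits event-free participants with follow-up to last dose + 98 days and states no cap at death, study exit or data cut-off, so exposure-adjusted AE rates can be biased low

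*SAP*

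**What the plan says.** Study C SAP 4.1 defines the treatment-emergent (TE) period as the "period from the first IMP administration to the last IMP administration + 98 days". Section 4.7.2 uses it twice for participants without an event. For exposure-adjusted rates, "for participants without an event, patient-years will correspond to the length of the TE period". For hazard ratios, "Participants without an event will be censored at the end of the treatment-emergent period in the Cox model". Section 4.7.2 also plans the same type of rate for AESIs and other AE groupings: "The exposure adjusted incidence rate by selected SMQ/CMQ and PT showing the number of participants with at least one TEAE per 100 patient-years".

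On timing, Study C SAP 4.9 says that "a primary database lock will be performed when all randomized participants in this study have completed their 24-week treatment phase", and that the CSR analysis uses data collected up to that lock. It adds that the database will be updated at the end of the study with the post-treatment follow-up, and that "Additional data between this database lock and last participant completing last visit will be summarized in a CSR addendum". Protocol 8.3.1 collects AEs from consent to the end-of-study visit. After that, sites report only related SAEs that they happen to learn of.

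The dates needed for a cap are already defined. Section 4.1 sets a separate on-study period that runs "until the end of the study defined as the status date collected on e-CRF page". Section 4.4.2 uses the status date for time to first OCS, where participants without the event "will be censored at Day 169 or their status date collected on the completion of study/follow-up eCRF form, whichever is earlier".

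**The concern.** The numerator of these rates holds only events that were observed and collected. The denominator, as written, holds the full TE period of every event-free participant, whether or not that time was observed. Two groups are over-credited:

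- participants still in post-treatment follow-up when the data are cut;
- participants who die or leave the study before last dose + 98 days.

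In both, unobserved time counts as event-free follow-up and the rate falls. The error runs one way only. The Study A and Study B version histories say that exposure-adjusted summaries were added on Health Authority recommendation, and the Study B one gives differing exposure between patients as the reason. Crediting time that nobody observed works against that purpose. At stake are the absolute rates per 100 patient-years for TEAEs, AESIs and AE groupings in the primary CSR.

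**Working it through.** The plan states no patient-year total or exposure-adjusted rate, so there is no figure of its own to reproduce.

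**Timeline (Protocol 1.3; Study C SAP 5.4, Table 9)**

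- q2w: planned last dose Week 22 = Day 155; 155 + 98 = Day 253, the Week 36 target day. Week 24 is Day 169. Largest gap at the lock: 253 − 169 = 84 days.
- q4w children under 30 kg: last dose Week 20 = Day 141; 141 + 98 = Day 239. Largest gap: 239 − 169 = 70 days.
- Early study exit or death: up to 98 days.
- Participants who reach the end-of-study visit before the lock, and those who stop treatment but stay in the study as Protocol 7.1.1 asks, add no material excess.

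**Lock part**

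Accrual length and lock lag are not in the documents, so both are assumed. Let R be accrual in weeks (uniform) and L the weeks from the last Week 24 visit to the lock. The remaining gap is g = 84 − 7L days (zero from L = 12). The mean unobserved time per participant is s = g²/(2 × 7R). Full credit is 253 − 1 = 252 days, so for a rare event person-time is inflated by s/(252 − s).

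Worked case, R = 52 and L = 0: s = 84²/728 = 9.69 days; 9.69/242.31 = 4.0%. The share still in follow-up is 84/364 = 23%, about 35 of 150.

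| Lag (weeks) | R = 52 | R = 78 | R = 104 |
|---|---|---|---|
| 0 | 4.0% | 2.6% | 2.0% |
| 4 | 1.7% | 1.2% | 0.9% |
| 6 | 1.0% | 0.6% | 0.5% |
| 8 | 0.4% | 0.3% | 0.2% |
| 12 or more | 0 | 0 | 0 |

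These figures assume that everyone is dosed to Day 155. Treatment stoppers who stay have an earlier TE end, so the true values are slightly lower.

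**Study-exit part**

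The exit share p and its timing are assumed. Take last dose uniform over doses 1 to 11 (mean 70 days after the first) and exit 14 days later. Credited time is 70 + 98 = 168 days; observed time is 70 + 14 = 84 days. On complete follow-up, inflation is (252 − 84p)/(252 − 168p) − 1 = 84p/(252 − 168p).

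- p = 2%: 1.68/248.64 = 0.7%
- p = 5%: 4.2/243.6 = 1.7%

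This part remains when follow-up is complete.

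**Both parts, R = 52**

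Inflation = (252 − 84p)/((1 − p)(252 − s) + 84p) − 1.

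- L = 6, p = 2%: 250.32/246.27 − 1 = 1.6%
- L = 0, p = 5%: 247.8/234.39 − 1 = 5.7%

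**Scale**

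An event with 5% risk over 252 days has a rate of 7.4 per 100 patient-years. With R = 52, L = 0 and no exits, the literal rule gives 7.15. Such an event yields about 4 cases in an arm of 75, for which exact Poisson 95% limits are 0.27 to 2.56 times the estimate.

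**Hazard ratio (simulation, R = 52, L = 6, 10% placebo event risk)**

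- 10% leaving in each arm, true value 2: 1.998 as planned, 2.000 with a cap.
- Assumed 15% placebo and 5% dupilumab leaving, true value 1: 1.040 as planned, 1.002 with a cap.

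**The case against.** The strongest reply is that Study C SAP 4.1 presents the TE period as one segment of an observation period, and that time after death, exit or the lock is not observation. A programmer might therefore truncate without being told. That is possible, but the text does not say so. The observation period is given no end, and the on-study period ending at the status date is defined separately and not used in 4.7.2. The time-to-OCS rule shows that the SAP writes an exit cap where it wants one, and the matching Study B rule (Study B SAP 4.4.2) adds the cut-off date as well.

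A second reply is that the lock effect may be nil. This stands. Section 4.9 sets a condition for the lock, not a date, and a lag of 12 weeks or more removes that part. The end-of-study database update would also supply the missing follow-up, although recomputation of the rates is not stated.

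A third reply is that little depends on it. This largely stands too. Section 4.7 makes safety descriptive with no testing. Counts, percentages and risk differences do not use this denominator. The lock part is balanced across arms.

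A reader might also take the 10% dropout in the sample-size section as a study-exit rate, which would push the combined figure to 7.6% (R = 52, no lag), or about 12% with 26-week accrual. The documents do not support that. The 10% is a sample-size assumption, Protocol 7.1.1 follows treatment stoppers to scheduled completion, and Protocol 7.2 expects withdrawal from the study to be uncommon.

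**Conclusion.** The point holds as a minor one: the rule is wrong as written. Applied literally, exposure-adjusted TEAE, AESI and AE-grouping rates in the primary CSR can be biased low and cannot be biased high. The lock part runs from zero to about 4% of person-time, and exits of 2% to 5% alone add about 0.7% to 1.7%. Accrual, lag, exit share and exit timing are all assumptions, and larger values need less plausible ones.

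A reader might infer that the reported rates will certainly be too low, or that comparisons between arms are distorted. Neither follows. The first depends on literal programming together with a lock before follow-up is complete, or with early exits or deaths. The second needs study exit to differ by arm, and even the assumed 15% against 5% moves a null hazard ratio only to about 1.04. The shift is also small beside sampling error for uncommon events. It is still a one-directional error that is easily avoided.

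**What to change.** In Study C SAP 4.7.2, state that for participants without an event both patient-years and Cox censoring end at the earliest of:

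- last IMP + 98 days;
- death;
- end-of-study or last-contact date;
- the data cut-off of that analysis.

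Apply the same rule to the AESI and other AE-grouping rates. State whether the rates are recomputed on complete follow-up for the CSR addendum. The Study A and Study B SAPs carry the same wording in their 4.7.2, so use the same cap if their rates are pooled with Study C or re-reported.

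The cost is one sentence and one derived censoring date, from dates already collected. Reported rates would be unchanged or slightly higher.
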